2. STUDY SUMMARY TABLE

STUDY TITLE:

Efficacy of Intravenous Steroid Boluses Combined with Oral Steroid Treatment Compared to Oral Steroids Alone for Moderate Ulcerative Colitis: A Multicenter, Randomized Clinical Trial

PROTOCOL CODE:

CECUM

EUDRA CT Number:

2016-001170-15

ClinicalTrials.gov Identifier:

NCT02921555

STUDY DESIGN:

Phase IV, controlled, prospective, randomized, open, multicenter study.

STUDY OBJECTIVE:

To compare the short- and long-term efficacy of adding three intravenous boluses of 0.5g of methylprednisolone to a conventional course of oral steroids (prednisone) for the treatment of moderate ulcerative colitis flares.

PRIMARY OUTCOME MEASURE:

Clinical and endoscopic remission, steroid-free at 8 and 54 weeks, without rescue treatment and without steroid requirement up to week 54.

STUDY POPULATION:

148 patients with moderate ulcerative colitis activity, with or without maintenance treatment or oral/topical mesalazine, will be stratified based on disease onset and maintenance treatment with mesalazine >2g/day in the last 3 months, and randomized 1:1 into the two treatment arms.

3. STUDY SUMMARY

Study Title:

Efficacy of Intravenous Steroid Boluses Combined with Oral Steroid Treatment Compared to Oral Steroids Alone for Moderate Ulcerative Colitis: A Multicenter, Randomized Clinical Trial.

Protocol Code:

CECUM.

EUDRA CT Number:

2016-001170-15.

ClinicalTrials.gov Identifier:

NCT02921555.

Study Design:

Phase IV, controlled, prospective, randomized, open, multicenter study.

Study Sites:

The study will be conducted at Spanish sites (Annex 1).

Study Objectives:

Primary Objective:

To compare the short- and long-term efficacy of adding three boluses of 0.5g methylprednisolone to a conventional course of oral steroids (prednisone) for the treatment of moderate ulcerative colitis flares.

Secondary Objectives:

- Clinical response at days 3 and 7.
- Biological response (C-reactive protein, fecal calprotectin) at days 3, 7, 2 months, and 12 months.
- Rate of adverse effects.
- Rate of severe adverse effects.
- Proportion of patients with clinical relapse.
- Time to clinical relapse.
- Need for hospitalization.
- Proportion of patients developing corticosteroid dependency.
- Time to development of corticosteroid dependency.
- Identification of predictive parameters of corticosteroid response.

Primary Outcome Measure:

Clinical and endoscopic remission, steroid-free at weeks 8 and 54, without rescue treatment and without the need for steroids until week 54.

Study Population and Sample Size:

148 patients with moderate activity ulcerative colitis, without maintenance treatment or with oral/topical mesalazine treatment, will be stratified based on disease onset and

maintenance mesalazine treatment at doses >2g/day in the past 3 months and randomized 1:1 into two treatment arms.

Study Treatment:

Treatment Groups:

1. **Intravenous bolus of 0.5 g/day of methylprednisolone for 3 consecutive days**, followed by oral prednisone 60 mg/day with a tapering regimen (decrease by 10 mg per week until a dose of 20 mg. From 20 mg, decrease by 5 mg per week until completely withdrawn).
2. **Oral prednisone at a dose of 60 mg/day for one week**, followed by a tapering regimen (decrease by 10 mg per week until a dose of 20 mg. From 20 mg, decrease by 5 mg per week until completely withdrawn).

In both groups, the study treatment will be accompanied by:

- Concomitant treatment with 1g/day 5-ASA suppositories for the first 4 weeks.
- Concomitant treatment with calcium (1000 mg/day) and vitamin D (800 IU/day) until the withdrawal of corticosteroids.
- Maintenance treatment with mesalazine 2 g/day starting from a reduction to 20 mg/day of prednisone (for patients on 5-ASA at the time of the flare-up, it will be suspended at study inclusion).

Study Duration:

156 weeks.

Timeline:

Start date: Q4 2018; End date: Q4 2021.

5. JUSTIFICATION

I) Summary of Relevant Non-Clinical and Clinical Findings for the Current Study

Ulcerative colitis (UC) is a chronic inflammatory bowel disease of unknown cause, characterized by flares or periods of active disease alternating with periods of remission or inactivity. Treatment is primarily based on the use of salicylic acid derivatives,

corticosteroids, immunosuppressants, anti-TNF antibodies, and anti-integrin antibodies. The management of flares depends on both the extent of the disease and the severity of symptoms. It is well-established that mild flares are treated with aminosalicylates, while severe flares require hospitalization and intensive treatment with intravenous corticosteroids. According to recommendations from the European Crohn's and Colitis Organization (ECCO), the treatment for moderate UC flares should also rely on aminosalicylates, with oral corticosteroids used as rescue therapy when there is no improvement with aminosalicylates. However, in clinical practice, many of these patients already receive maintenance therapy with aminosalicylates (often at high doses), making oral corticosteroids the initial treatment option in most cases. Nonetheless, the efficacy of oral corticosteroids for moderate flares has been scarcely evaluated, with reported success rates between 30% and 50% in limited randomized controlled trials (2-5).

In clinical practice, intravenous corticosteroids are frequently used for moderate flares. There is evidence suggesting that intravenous administration may have greater efficacy in moderate UC activity. A retrospective study conducted in our setting showed that in UC patients who responded to an initial course of corticosteroids, intravenous administration during moderate flares was associated with a lower relapse rate (61% compared to 80%, $p=0.027$) (6). This high relapse and/or corticosteroid dependency rate may be related to achieving clinical remission without endoscopic remission (7).

Pharmacokinetic data also support the use of intravenous corticosteroid treatment for UC flares. A study over 30 years ago demonstrated that plasma concentrations of prednisolone after oral administration were significantly lower in patients with severe UC flares compared to healthy subjects (8). Among patients with severe UC flares, plasma prednisolone levels after intravenous administration of 20 mg were higher (peak and area under the curve) compared to oral administration of 40 mg (9). Moreover, a retrospective study (10) suggested that intravenously administered corticosteroids for moderate UC flares are more effective at inducing clinical remission than the oral administration of 40 mg prednisone in controlled trials (2-5). Patients who initially failed to respond to oral corticosteroids but later responded to intravenous administration were more likely to develop corticosteroid dependency during follow-up than those treated intravenously from the outset for moderate activity (54% vs. 23%, $p=0.01$) (10).

II) Description and Justification of the Administration Route, Dosage, Regimen, and Treatment Period

Our hypothesis suggests that in moderate UC flares, corticosteroids administered intravenously are more effective than when administered orally, likely because they induce mucosal healing in a higher proportion of patients. This would result in a greater initial endoscopic remission rate and a lower rate of relapses and/or development of corticosteroid dependency in the medium term compared to conventional oral treatment. In other immune-mediated inflammatory diseases requiring rapid response, such as lupus nephritis or acute transplant rejection, high-dose intravenous corticosteroid boluses have shown superior outcomes compared to conventional oral prednisone regimens (11-12).

Corticosteroid bolus therapy consists of administering supraphysiological doses of corticosteroids over a short period (2 to 5 days) without a subsequent tapering schedule. This therapeutic approach has been associated with a prolonged therapeutic effect without the feared adverse effects typically seen with corticosteroid therapy. In UC, four studies have reported results on corticosteroid boluses (two of which were retrospective studies in pediatric patients, one in severe UC, and one in moderate UC). These studies, with limited patient numbers and varying regimens (mainly involving oral corticosteroids after the initial boluses), suggested a faster therapeutic effect without an increase in adverse effects (13-16). This strategy may allow for outpatient intravenous corticosteroid administration, avoiding hospital admissions typically required in clinical practice, without increasing the risk of adverse events.

Treatment Groups:

1. **Intravenous Bolus Group:** 0.5 g/day of methylprednisolone for 3 consecutive days, followed by oral prednisone at 60 mg/day for one week, then a tapering regimen (decrease by 10 mg weekly until a dose of 20 mg, followed by a decrease of 5 mg weekly until complete withdrawal).
2. **Oral Prednisone Group:** 60 mg/day for one week, followed by a tapering regimen (decrease by 10 mg weekly until a dose of 20 mg, followed by a decrease of 5 mg weekly until complete withdrawal).

In both groups:

- Concomitant treatment with 1g/day 5-ASA suppositories during the first four weeks.
- Concomitant treatment with calcium (1000 mg/day) and vitamin D (800 IU/day) until corticosteroids are withdrawn.
- Maintenance treatment with mesalazine 2-2.4 g/day starting from the reduction to 20 mg/day of prednisone (for patients on 5-ASA at the time of flare-up, this will be stopped at study inclusion).
- Any other concomitant treatment the patient receives during the study must be documented in the e-CRD.

III) General and Specific Guidelines for Investigators

Investigators must strictly adhere to the protocol and completely fill out the electronic data collection form (e-CRD) provided by the sponsor.

The trial will be conducted in accordance with the recommendations for clinical trials and the evaluation of drugs in humans, as outlined in the Declaration of Helsinki (1964), and its revisions in Tokyo, Venice, Hong Kong, South Africa, Edinburgh, Washington, Tokyo, and Seoul (2008), Good Clinical Practice (GCP) standards, and current Spanish legislation (Royal Decree 1090/2015) on clinical trials.

If any participant experiences a disease or adverse event that requires pharmacological treatment or modifies the study drugs' disposition, the study medication must be withdrawn. In such cases, the adverse event will be monitored until resolution and the participant followed up until the end of the study. If the adverse reaction is mild or moderate and does not require suspension of the drug, it will be documented, and the study will continue as planned.

IV) Study Population Description

A total of 148 patients with moderate activity ulcerative colitis, without maintenance treatment or with oral/topical mesalazine, will be stratified based on disease onset and maintenance treatment with mesalazine at doses >2g/day in the last three months and randomized 1:1 into two treatment arms.

V) Literature References and Relevant Data

Recommendations of the European Crohn's and Colitis Organization governing clinical practice in ulcerative colitis treatment.

(Additional references 2-16 as listed in the original protocol are summarized and referenced in the document for completeness.)

6. OBJECTIVES AND PURPOSE OF THE STUDY

Primary Objective

To compare the short- and long-term efficacy of adding three intravenous boluses of 0.5g of methylprednisolone to a conventional course of oral corticosteroids (prednisone) for the treatment of moderate ulcerative colitis flares.

Secondary Objectives

- Clinical response at days 3 and 7.
- Biological response (C-reactive protein, fecal calprotectin) at days 3, 7, 2 months, and 12 months.
- Rate of adverse effects.
- Rate of severe adverse effects.
- Proportion of patients with clinical relapse.
- Time to clinical relapse.
- Need for hospitalization.
- Proportion of patients developing corticosteroid dependency.
- Time to development of corticosteroid dependency.

- Need for and time to surgery.
- Identification of predictive parameters of corticosteroid response.

7. STUDY DESIGN

I) Primary and Secondary Variables

Primary Outcome Variable:

Clinical and endoscopic remission, steroid-free at 8 and 54 weeks, without rescue treatment and without the need for steroids up to week 54.

Secondary Variables (Variables of Interest):

- **Clinical Remission** (assessed at weeks 8 and 54): Mayo Score \leq 2 points with no individual variable $>$ 1.
- **Endoscopic Remission**: Mayo endoscopic subscore of 0 or 1.
- **Clinical Response** (assessed at weeks 8 and 54): a reduction in the Mayo score by at least 3 points and at least 30%, with a decrease in the rectal bleeding subscore of at least 1 point or to an absolute value of 0 or 1.
- **Early Clinical Response**: a decrease in the clinical Mayo subscore by at least 3 points and at least 30%, with a decrease in the rectal bleeding subscore of at least 1 point or to an absolute value of 0 or 1, at days 3 and 7 of corticosteroid treatment.
- **Relapse**: reappearance of symptoms, defined as a Mayo clinical subscore $>$ 2. The time of relapse from treatment initiation will be recorded.
- **Corticosteroid Dependency**: relapse during prednisone tapering or within three months after corticosteroid discontinuation.
- **Rescue Treatment**: restart or increase of the established corticosteroid dose (including topically acting oral corticosteroids) or initiation of any treatment for ulcerative colitis other than mesalazine, including biological agents (infliximab, adalimumab, golimumab, vedolizumab), calcineurin inhibitors (cyclosporine, tacrolimus), thiopurines (azathioprine, mercaptopurine), methotrexate, leukapheresis, or colectomy.
- **Need for Surgery** and time to surgery from treatment initiation.
- **Adverse Event Rate** and rate of severe adverse events (including hospitalizations) recorded throughout the study duration.
- **Fecal Calprotectin Determination**.

II) Study Design

This is a Phase IV, controlled, prospective, randomized, open, multicenter study to compare two corticosteroid treatment regimens for moderate UC flares.

III) Estimated Number of Subjects, Sample Size, and Justification

Study Subjects: Adult patients of both sexes with active moderate ulcerative colitis, with or without maintenance treatment or with oral/topical mesalazine.

Sample Size: 148 patients.

Sample Size Calculation:

Assuming a probability of clinical and endoscopic remission at 8 weeks and sustained without corticosteroid reintroduction or rescue treatment at 54 weeks of 20% in the control group (oral prednisone), a total of 148 patients are needed to detect a $\geq 20\%$ improvement in the therapeutic group (one-tailed test) with a significance level (α) of 0.05 and a power (β) of 0.20, accounting for an estimated 10% dropout rate.

IV) Randomization and Blinding Techniques

After the patient signs the informed consent document approved by the Research Ethics Committee and AEMPS, and meets all inclusion criteria and none of the exclusion criteria, they will be eligible for inclusion in the trial. Patients will be randomized (1:1) into each treatment arm via a computerized system provided by AEG-RedCap. Randomization will be performed in blocks of 4 and stratified by (1) whether the disease is newly diagnosed, and (2) whether the patient has received maintenance treatment with mesalazine at doses > 2 grams/day in the last three months.

This is an open-label study, meaning both the study subjects and investigators will be aware of the assigned treatment. However, blinding will be maintained in the analysis of blood samples for corticosteroid response predictive factors and calprotectin levels in fecal samples, which will be centralized and blinded. The technician conducting the measurement will not know the treatment arm or the clinical response associated with each sample.

V) Treatment Description

The study medication (methylprednisolone for intravenous bolus) will be supplied by the sponsor, while the oral prednisone, calcium supplements, and aminosalicylates will be supplied as per routine clinical practice.

Treatment Groups:

1. **Intravenous Bolus Group:** 0.5 g/day of methylprednisolone administered intravenously for 3 consecutive days, followed by oral prednisone 60 mg/day for 1 week, with a subsequent tapering regimen (decrease by 10 mg weekly until 20 mg, followed by a decrease of 5 mg weekly until complete withdrawal).
2. **Oral Prednisone Group:** 60 mg/day for 1 week, followed by a tapering regimen (decrease by 10 mg weekly until 20 mg, followed by a decrease of 5 mg weekly until complete withdrawal).

In both groups:

- **Concomitant 5-ASA Suppository Treatment:** 1g/day during the first 4 weeks.
- **Calcium and Vitamin D Supplementation:** Calcium 1000 mg/day and Vitamin D 800 IU/day until corticosteroid withdrawal.
- **Maintenance Mesalazine Treatment:** Mesalazine 2-2.4 g/day starting from prednisone tapering to 20 mg/day (in patients receiving 5-ASA during the flare-up, it will be discontinued upon inclusion in the study).

- Any other concomitant treatment received by the patient during the study must be recorded in the e-CRD.

Study Procedures: (summarized in Annex 8)

1. Inclusion and exclusion criteria will be reviewed, and informed consent will be signed at Visit 0.
2. Pre-inclusion epidemiological and clinical data will be collected.
3. Anthropometric data: height and weight, taken at the screening visit (V0).
4. Stool sample collection (Clostridium Difficile toxin determination and coproculture) and pregnancy test for women at the screening visit (V0).
5. Vital signs (temperature, heart rate, and blood pressure) and basic physical examination at each visit (V0 to V8).
6. Disease Activity Index according to the Mayo Clinic score (Disease Activity Index – DAI, Annex 2) will be calculated at visits V1, V5, and V8, and clinical subscore will be calculated at all other study visits. Walmsley Index will be calculated at all visits (Annex 3).
7. General laboratory tests (including blood count, renal and liver function, and C-reactive protein) and fecal sample collection for fecal calprotectin determination (samples preserved frozen until study completion for centralized analysis) at each visit.
8. Blood sample collection at baseline for corticosteroid response predictive factors analysis.
9. Rectosigmoidoscopy and Mayo endoscopic subscore calculation (Annex 2) at Visits V0 or V1, V5, and V8.
10. Clinical response assessment at Visits V2 and V3; clinical and endoscopic response assessment at Visits V5 and V8.
11. **Extra Visit for Intravenous Bolus Group (Group 1):** an additional visit on Day 2 (Visit 1.1) for administration of the second corticosteroid bolus.

VI) Recruitment Period, Follow-Up, and Study Duration

- **Patient Inclusion Start Date:** September 2018
- **Patient Inclusion End Date:** September 2020
- **Recruitment Period:** 104 weeks
- **Patient Treatment Duration:** 8 weeks
- **Patient Follow-Up Duration:** 42 weeks
- **Expected Completion Date for Last Enrolled Patient:** September 2021
- **Total Study Duration:** 156 weeks
- **Duration of Patient Participation:** 12 months

VII) Criteria for Premature Study Termination and Interruption

Criteria for Premature Study Termination:

- **Patient Decision:** Patients may withdraw from the study at any time without any penalty or impact on their disease management or subsequent required treatments.
- **Serious Complications Due to Steroid Treatment:** Occurrence of severe adverse events related to corticosteroid treatment.

- **Lack of Early Clinical Response.**
- **Lack of Clinical and Endoscopic Remission, Steroid-Free at Week 8.**
- **Clinical Worsening and Need for Rescue Treatment or Serious Adverse Event:** At the investigator's discretion, this can occur at any time during the study.

VIII) Procedures to Verify Adherence to Oral Treatment

This procedure is intended to determine the study medication adherence of the subjects. The principal investigator or a delegated person will provide detailed instructions to the patient regarding medication intake, along with an informative medication diary to be returned upon treatment completion (see Annex 6). Therefore, the principal investigator or delegated personnel must maintain product traceability and record medication administration per patient visit in the electronic case report form (e-CRD). Any medication-related incidents must be documented in the patient's clinical history and recorded in the e-CRF.

IX) Blinding Techniques

This is an open-label study, meaning no blinding will be applied except for the analysis of blood samples for predictive factors of corticosteroid response and the determination of fecal calprotectin in collected fecal samples. These analyses will be conducted centrally and blinded to ensure the laboratory technician performing the analysis is unaware of the treatment group and the patient's clinical response.

Evaluation of the primary outcome variable will be performed by the endoscopy services of the participating hospitals. Endoscopists will conduct a blinded assessment of endoscopic procedures (third-party blinded evaluations).

X) Data Identification

Investigators will comply with GCP standards. All information collected during the trial will be documented in the electronic case report form (e-CRF). In case of any protocol deviations, they will be limited to that specific patient. The investigator(s) will comprehensively document the deviation and its reason in the e-CRF. If a deviation pertains to inclusion/exclusion criteria, investigators must contact the clinical monitor to inform them by phone.

XI) Definition of Study End

The study end date is defined as the date when the last patient completes their final follow-up visit.

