8. SUBJECT SELECTION AND WITHDRAWAL

I) Inclusion Criteria

1. Diagnosis of Ulcerative Colitis based on the European Crohn's and Colitis Organization criteria.
2. Patients aged 18 years or older.
3. Disease extension of at least left-sided (involvement >25 cm from the anal margin).
4. Moderate flare according to the Mayo Index (score ≥ 6 and ≤ 10).
5. No maintenance treatment or only 5-ASA oral and/or topical treatment.
6. Patient has the capacity to understand study requirements and provide informed consent.
7. Signed Informed Consent.

II) Exclusion Criteria

1. Previous or current treatment with thiopurines, calcineurin inhibitors, methotrexate, and/or biological agents.
2. Systemic corticosteroid use in the last 6 months (excluding topical oral corticosteroids).
3. Severe active or uncontrolled systemic infection, serious diseases, or medical conditions that may interfere with the patient's eligibility or treatment.
4. Uncontrolled diabetes mellitus or hypertension.
5. Psychiatric disorder or any other uncontrolled condition that contraindicates steroid treatment.
6. Pregnancy, lactation, or intention to become pregnant during the study period.
7. History of allergic reactions attributed to corticosteroids.

III) Withdrawal Criteria and Analysis

Premature termination of the trial will occur whenever the clinical trial is terminated before meeting the conditions outlined in the protocol.

Patients may be withdrawn from the study before reaching week 54 (end of follow-up) for any of the following reasons:

- **Patient Decision:** Patients are free to withdraw from the study at any time without any penalty or impact on their disease management or subsequent treatments.
- **Pregnancy.**
- **Serious Complications Due to Steroid Treatment.**
- **Lack of Early Clinical Response.**
- **Failure to Achieve Clinical and Endoscopic Remission, Steroid-Free at Week 8.**
- **Clinical Worsening and Need for Rescue Treatment at the Investigator's Discretion.**
- **Major Protocol Deviation.**

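### As written, the rectal bleeding clause of both response definitions demands a fall in either branch, so some patients in full remission are scored non-responders (minor; secondary endpoints)

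*Combined protocol and SAP*

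**What the plan says.** Section 7.I (Primary and Secondary Variables) gives two response definitions.

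- **Clinical Response**, weeks 8 and 54: "a reduction in the Mayo score by at least 3 points and at least 30" per cent.
- **Early Clinical Response**, days 3 and 7: "a decrease in the clinical Mayo subscore by at least 3 points and at least 30" per cent.

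Both carry the same added condition: "with a decrease in the rectal bleeding subscore of at least 1 point or to an absolute value of 0 or 1".

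The same section defines Clinical Remission by follow-up scores alone, as a total Mayo score of at most "2 points with no individual variable" above 1. It needs no change from entry and allows a bleeding subscore of 0 or 1. Endoscopic Remission is a "Mayo endoscopic subscore of 0 or 1".

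The activity criterion for entry in section 8.I is "Moderate flare according to the Mayo Index", with a total from 6 to 10. No inclusion or exclusion criterion sets a minimum bleeding subscore.

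Response is used in four places. "Clinical response at days 3 and 7" is the first secondary objective in sections 3 and 6. Response at weeks 8 and 54 is a variable of interest in section 7.I. Early response is an outcome in the association and logistic regression analyses of section 12.I. Lack of early response is also among the reasons for stopping or withdrawal in sections 7.VII and 8.III.

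**The concern.** Read grammatically, the clause offers two kinds of decrease: one of a given size, and one that ends at a given level. Either way the subscore must fall. A patient whose bleeding is already absent has nothing left to lose and fails the clause whatever happens to the other items. A patient with a bleeding subscore of 1 that stays at 1 fails as well, although remission accepts that value.

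Remission is the stricter state and should imply response. Under this text it does not, so a table could show a patient as a remitter and a non-responder at the same visit. The second alternative also becomes redundant, which suggests that the authors meant something else. Two programmers could reasonably code the clause differently. In an open-label trial that choice should not be left until the data are visible.

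**Working it through.** There is no stated figure to reproduce, because the point concerns the logic of a definition.

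**Inputs.** The response, remission and entry rules are those given above. One assumption is needed: the Mayo score has four whole-number items (stool frequency, rectal bleeding, endoscopy, physician's assessment), each 0 to 3. Annex 2, which holds the index, is not in the text available for review.

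**Step 1: is the second branch redundant?** Let B be entry bleeding and F follow-up bleeding. As written, the clause is (B − F ≥ 1) or (B − F > 0 and F ≤ 1). For whole numbers B − F > 0 means B − F ≥ 1, so the clause reduces to B − F ≥ 1. The alternative reading is (B − F ≥ 1) or (F ≤ 1).

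**Step 2: which entry profiles are possible?** With B fixed, the other three items must sum to between 6 − B and 10 − B.

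- B = 0: sums 6, 7, 8, 9 give 10 + 6 + 3 + 1 = 20 profiles.
- B = 1: sums 5 to 9 give 12 + 20 = 32.
- B = 2: sums 4 to 8 give 12 + 12 + 10 + 6 + 3 = 43.
- B = 3: sums 3 to 7 give 10 + 12 + 12 + 10 + 6 = 50.

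The total is 145.

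**Step 3: which follow-up profiles are in remission?** With a total of at most 2 and no item above 1, there are 1 + 4 + 6 = 11. Of these, 7 have F = 0 and 4 have F = 1. All 11 have an endoscopic item of 0 or 1, so endoscopic remission is met too.

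**Step 4: is the total-score part met?** The smallest possible reduction is 6 − 2 = 4 points, which is 67% of 6. All 145 × 11 = 1,595 pairs meet the 3-point and 30% conditions. Only the bleeding clause can fail them.

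**Step 5: apply the clause to the remission pairs.**

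| Entry bleeding | Pairs | Non-response as written | Non-response, alternative reading |
|---|---|---|---|
| 0 | 20 × 11 = 220 | 220 | 0 |
| 1 | 32 × 11 = 352 | 32 × 4 = 128 | 0 |
| 2 or 3 | 93 × 11 = 1,023 | 0 | 0 |
| All | 1,595 | 348 | 0 |

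**Worked records.**

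- Entry: frequency 2, bleeding 0, endoscopy 2, physician 2 (total 6). Week 8: all items 0. The reduction is 6 points (100%) and both remissions are met, but B − F = 0, so this is non-response.
- Entry: 2, 1, 2, 2 (total 7). Week 8: bleeding 1, the rest 0. The total falls by 6 to 1 and both remissions are met, but B − F = 0, so this is non-response. Had bleeding fallen to 0, it would count as response.

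**Early response.** The table covers the total-score definition only. The bleeding clause is identical at days 3 and 7, so entry bleeding 0 again excludes response. If the clinical subscore is the total without endoscopy, all 20 profiles with B = 0 have a clinical subscore of at least 6 − 3 = 3. The 3-point fall is then attainable, and the bleeding clause alone blocks response.

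**The case against.** The strongest reply is that this is a wording slip with a fairly evident meaning. A programmer who wants both halves of the clause to do something arrives at the alternative reading, and nothing in the documents shows the literal rule being applied. The text may also render another version of the protocol (section 5.V refers to an original), and whether the slip exists there cannot be checked. This is fair and keeps the point minor. It does not remove it: the text in hand gives a wrong result if followed, and no other section corrects it.

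For entry bleeding 1 the defect is partial, since 352 − 128 = 224 of the 352 pairs do count as response. It bites only when bleeding stays at 1.

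Three stronger readings are tempting, and the documents do not support them.

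- **That the rule shrinks the treatment difference and costs power.** Every input would have to be invented. Suppose 5% enter with bleeding 0, 20% enter with bleeding 1, true response is 40% v 60%, and 20% to 40% of responders entering at 1 stay at 1. A common loss of 0.05 + 0.20 × 0.20 = 9% to 0.05 + 0.20 × 0.40 = 13% in both arms would lower two-sided 5% power at 74 per arm from 0.69 to between 0.61 and 0.57. But staying at 1 is itself a treatment outcome. With 40% staying in the oral arm and 20% in the bolus arm, the rates are 0.40 × 0.87 = 34.8% and 0.60 × 0.91 = 54.6%. The difference is 19.8 points and power is 0.68, practically unchanged. The answer depends on quantities that the documents do not give.
- **That the primary outcome is wrong.** It rests on remission (sections 7.I, 10.I and 12.I), as do the sample size and the interim rule.
- **That misclassified patients will become primary failures**, by being withdrawn for lack of early response and then imputed as non-response (section 12.I). That route is possible but indirect. The documents do not show that withdrawal follows mechanically from the derived variable.

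**Conclusion.** The point holds as a minor error in two secondary definitions. As written, a patient entering with bleeding 0 can never be a responder, and one entering at 1 and staying at 1 is a non-responder, whatever else improves. Remission is therefore not a subset of response. Clinical response at weeks 8 and 54, early response at days 3 and 7 and the predictor analysis of early response are affected.

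The redundancy needs only a whole-number item; the counts also need the 0 to 3 scoring. The counts describe possible score combinations, so 348 of 1,595 must not be read as a share of patients. The share entering a moderate flare with bleeding 0 or 1 is not in the documents. The practical effect is unknown and probably small, and no claim about power or the difference between arms should be made from it. The use of early response as a withdrawal reason has to be reconciled with whatever definition is adopted; how that rule should operate is for the sponsor.

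**What to change.** In both definitions in section 7.I, replace the bleeding clause with: *and either a decrease of at least 1 point in the rectal bleeding subscore or an absolute rectal bleeding subscore of 0 or 1 at the assessment visit*. Add a derivation check that every patient in clinical remission at week 8 or 54 is also a responder. Under the new wording this holds for all 1,595 pairs. Settle the wording before response is tabulated by arm, and have the sponsor reconcile sections 7.VII and 8.III with it.

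One consequence should be confirmed as intended. A patient who enters with bleeding 0 and has 1 at follow-up would count as a responder if the score reduction is met (20 × 4 = 80 of the remission pairs). This agrees with the remission definition, which also accepts a 1.

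The cost is one clause in two places and one line of code. No patients, visits or data are added.
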